The primary objectives of this trial will be to compare rates of self-reported, symptomatic volume GOR and objectively measured rates of volume GOR using scintigraphy, between the two study groups. This will be a superiority trial, with the hypothesis being that palliative oesophageal anti-reflux self-expanding fully covered metal stents significantly reduce volume GOR compared to conventional oesophageal self-expanding fully covered metal stents.

Secondary Objectives

Secondary objectives will be to compare outcomes, including rates of dysphagia, cough, pain, stentrelated complications, subsequent complications and patient survival at the end of the study period. A further objective will be to compare the self-reported GOR questionnaire (GerdQ) outcomes to the objectively measured oesophageal scintigraphy measurements.

METHODS

Trial Design

This study will be a prospective randomised controlled trial comparing anti-reflux oesophageal stents to conventional oesophageal stents. Randomisation to an anti-reflux stent versus a conventional stent will be done prior to stent placement and the patient will remain blinded to the type of stent placed. Although the authors will not be blinded to the stent type, as the stents are easily distinguished from each other at the time of endoscopy, the Clinical Coordinator who will be doing the follow-up will be blinded to this. This study will be performed following the CONSORT 2010 checklist of information for randomised trials ²².

Once the study is approved by the University of Cape Town's Human Research Ethics Committee, approval for the study will also be obtained from Groote Schuur Hospital. The trial will then be registered with the South African National Clinical Trials Register (SANCTR) and at clinicaltrials.gov. Both stents being compared in this trial are already approved by the South African Health Products

Regulatory Authority (SAHPRA), and as they form part of standard of care, application to SAHPRA will not be necessary.

Participants

Eligibility criteria for trial participants:

Inclusion Criteria (all criteria must be met):

- Adult patients 18 years of age or older
- Informed consent obtained from the patient after oral and written explanation of the trial
- Histologically confirmed malignancy of the distal oesophagus or OGJ
- Obstructive or irresectable malignancy due to metastases, local tumour infiltration or poor performance status

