- Once deployed, the distal end of the stent must have crossed the OGJ junction and be lying within the proximal stomach

Exclusion Criteria:

- Patient declining or unable to give informed consent, including inability to speak or understand either English, Afrikaans or isiXhosa.
- Patient unable to comply with the follow-up protocol of the trial (e.g. does not have a contactable telephone number)
- Oesophageal cancers selected for curative treatment or irresectable oesophageal cancers selected for palliative chemoradiation, but not requiring oesophageal stenting
- Benign oesophageal pathology or extrinsic compression of the oesophagus from another cause
- Patients with oesophageal cancers where the stent does not cross the OGJ
- Pregnant patients
- Patient performance status precluding any intervention or sedation

Setting and Location of Trial

This trial will take place at the Upper Gastrointestinal Surgery Unit at Groote Schuur Hospital (GSH). All stent insertions for the trial will be performed by either of the two full-time consultants working in the Upper Gastrointestinal Surgery Unit at GSH. Palliative oesophageal stenting is performed in the endoscopy suite in E23 under conscious sedation. After appropriate post-procedural observation in the unit, the patient will be admitted to the hospital for overnight observation and if deemed well enough, will be discharged home the following day after the scintigraphy.

Interventions

Patients considered eligible for the trial will be enrolled after obtaining informed consent. Oesophageal stenting will be performed according to standard practices at the GSH endoscopy suite using video endoscopy (standard gastroscope) and fluoroscopy. Patients will be appropriately sedated for the procedure, provided with supplemental oxygen and a diagnostic upper gastrointestinal endoscopy will then be performed to confirm the site and length of the histologically confirmed oesophageal cancer. Randomisation will then occur only if stenting is required which will result in OGJ overlap. Regardless of which type of stent the patient receives, all enrolled participants will be prescribed a twice daily dose of a proton pump inhibitor post the procedure, which is continued indefinitely as per the current standard of care at GSH.

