Randomisation will be done using opaque, sealed envelopes with computer-generated random numbers in blocks of 20 (10:10). Patients will be randomised to either receive a conventional oesophageal stent or an anti-reflux oesophageal stent. Other than the anti-reflux mechanism, all other parameters of the two stents will be the same – both stents will be fully covered Nitinol self-expanding metal stents designed for deployment in the oesophagus (conventional stent: Taewoong Niti-S Esophageal Covered Stent, distributor: First Medical Company [Global Medical Device Nomenclature Code 61751] and anti-reflux stent: Taewoong Niti-S Esophageal Covered AR Stent, distributor: First Medical Company [Global Medical Device Nomenclature Code 61751] and anti-reflux stent: Taewoong Niti-S Esophageal Covered AR Stent, distributor: First Medical Company [Global Medical Device Nomenclature Code 48136]). Both stent types come in a standard length of 120mm. Both of these stents are available and currently form part of the standard of care at GSH, although the stent selection is determined by stent availability and endoscopist preference – the conventional stent is generally favoured. Both are approved by SAHPRA as part of First Medical's list of approved devices they can import into and distributed in South Africa.

The technique of stent deployment will also be the same for both anti-reflux and conventional stents. Stent position and deployment success will be confirmed after stent placement, using water-soluble contrast injected through the stent under fluoroscopy – this will confirm the distal stent position crossing the OGJ. The patient will remain unaware of which type of stent they are receiving. The progress of the trial will be documented according to the CONSORT 2010 flow diagram²².

Follow-up

Technical success of the stent insertion will be confirmed using fluoroscopy immediately after insertion. Any insertion-related complications will be documented. All patients will be appropriately observed in the gastrointestinal unit after the procedure and then admitted to the ward for overnight observation. They will undergo scintigraphy the following day (day 1 post the procedure) and then if deemed well enough will be either discharged home or referred back to their referring hospital. The follow-up period will subsequently continue for a total of 8 weeks.

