Using a power calculation for comparison of two continuous data means in a superiority assessment (with GerdQ score means as the primary outcome assessed), assuming a 2-point reduction in GerdQ mean score between the two groups - mean GerdQ score of 9 in the conventional stent control group and a GerdQ score of 7 in the anti-reflux stent group - with a standard deviation of 3, with an alpha level of 5% and power set at 80%, a sample size of 72, with 36 in each arm, is required.

Correlating this to the previous randomised controlled trials, it is noted that these numbers are similar, but slightly higher than previous trials. With concerns that a number of these previous trials were underpowered, a slightly bigger sample size is deemed appropriate.

Time Frame

The study will begin as soon as HREC approval has been granted and the relevant registrations with SANCTR and clinicaltrials.gov have been completed. It is expected to run for 36 months. Interim analyses of the collected data will be performed at 12 and 24 months.

Budget

All research-related costs will be covered by the General Surgery and Surgical Gastroenterology Research Funds.

1. Stents:

Both types of oesophageal stents (conventional and anti-reflux) are currently available at Groote Schuur Hospital and as they form part of the standard treatment of these patients, will not need to be purchased specifically for this research study.

- Scintigraphy: R4000 per investigation x 72 patients = R288 000
- 3. Clinical coordinator:

The clinical coordinator for this trial is already employed by the University of Cape Town and is very active in multiple research projects within the Surgical Gastroenterology Unit. She will thus not need to be renumerated specifically for her assistance in this trial.

4. Other Costs:

This trial will not require specific electronic or other research-related equipment or major stationary costs. All other minor costs will be borne by the study investigators.

TOTAL COSTS:

R288 000

REFERENCES

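### One published block size of 20, with the last eligibility judgement made at endoscopy just before allocation, lets a well-informed operator know a few allocations in advance

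*Combined protocol and SAP*

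**What the plan says.** Under Interventions, a diagnostic endoscopy first confirms the site and length of the tumour. "Randomisation will then occur only if stenting is required which will result in OGJ overlap". Allocation follows at once: "Randomisation will be done using opaque, sealed envelopes" with "computer-generated random numbers in blocks of 20 (10:10".

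Under Setting and Location of Trial, every trial stent is placed by one of two consultants in one unit. Trial Design says "Although the authors will not be blinded to the stent type", because the two devices look different at endoscopy; the patient and the Clinical Coordinator are blinded. Interventions also records that, in usual practice, stent choice depends on availability and endoscopist preference, with the conventional stent the more usual choice.

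Sample Size states "a sample size of 72, with 36 in each arm, is required".

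The document does not say who generates the list, who holds or opens the envelopes, whether they are sequentially numbered, whether eligibility is recorded before opening, or what happens to an incomplete last block.

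**The concern.** Opaque envelopes hide the next card but do not prevent counting. When the block size is known and fixed, an operator who has seen the earlier stents can tell which arm is behind and, near the end of a block, sometimes exactly what comes next. If that person also judges whether stenting is required and whether the stent will overlap the OGJ, a borderline judgement could depend on the stent expected. The arms could then differ before treatment begins. Blinding the patient and the coordinator protects the outcome assessment, not this step, and the Statistical Analysis section specifies no baseline-adjusted GerdQ comparison that might absorb part of the difference.

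A smaller matter is that 72 is not a multiple of 20, so equal arms do not follow from the scheme.

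**Working it through.** **Inputs.** Block size 20, split 10:10 (Interventions). Total 72, 36 per arm; difference 2 points, SD 3, alpha 5%, power 80% (Sample Size).

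**1. The plan's own figure.** Two-sided normal approximation: n per arm = 2 × (1.96 + 0.8416)² × 3² / 2² = 35.3, rounded up to 36, so 72 in total. The stated number is reproduced. Power at 36:36 is Φ(2 / (3 × √(2/36)) − 1.96) = Φ(0.868) = 80.7%.

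**2. Allocations known with certainty.** These are the allocations left once one arm has used its 10 places. In a block of 2n the expected number is 2n/(n+1) = 20/11 = 1.82. Because 72 = 3 × 20 + 12, three full blocks give 3 × 1.818 = 5.45. The first 12 places of the fourth block add almost nothing. Total about 5.5 of 72, or 7.6%. This needs both the earlier allocations and the block size and boundaries.

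**3. Allocations guessed correctly.** The rule is to guess the arm that is behind. For a full block the expected number correct is n + ½(4ⁿ / C(2n,n) − 1) = 10 + ½(1,048,576/184,756 − 1) = 12.34 of 20 (61.7%). Three full blocks give 37.01. The last 12 places, summed over the hypergeometric states, give 6.66. Total 43.7 of 72 = 60.7%, against 36 by chance. This rule needs only the tally of earlier allocations, because the tally returns to zero at the end of every block.

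**4. What guessing could do (assumed shift, for scale only).** Suppose every guess is acted on, and the expected GerdQ of those enrolled moves up by d when one stent is expected and down by d when the other is. The bias in the arm difference is 2 × (2 × 0.607 − 1) × d = 0.43d. For d = 0.5, 1 and 1.5 it is 0.21, 0.43 and 0.64 points, against a target effect of 2. With a standard error of 0.707, the true two-sided error would be about 6%, 9% and 15%. The documents give no value for d.

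**5. Other block schemes, same guessing rule, 72 patients.**

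| Scheme | Correct guesses |
|---|---|
| Fixed 20 (as planned) | 60.7% |
| Fixed 12 | 64.3% |
| Fixed 4 | 70.8% |
| Varied 4/6/8 | 67.8% |
| Varied 8/10/12 | 64.8% |
| Varied 16 to 22 | 61.2% |

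The varied rows are simulated. Concealing the sizes does not defeat the tally rule; it removes most of the certainty in step 2, because an arm reaching a given count no longer shows that its places are used up.

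**6. Balance at 72.** The first 60 split 30:30. The last 12 follow a hypergeometric distribution (12 drawn from 10 and 10). P(36:36) = 210 × 210 / 125,970 = 35.0%. P(35:37 or 37:35) = 2 × 252 × 120 / 125,970 = 48.0%. P(gap of 4 or more) is the remaining 17.0%. The worst split is 32:40, with power Φ(2 / (3 × √(1/32 + 1/40)) − 1.96) = 80.3%, against 80.7% at 36:36.

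**The case against.** Several points on the other side are sound.

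- A block of 20 is already among the less guessable blocked schemes. A reader might infer that smaller blocks are the cure, or that varying and hiding sizes is enough. Step 5 shows otherwise: small blocks raise guessing even when varied. This stands, and it shapes the fix.
- The 7.6% and 61% assume complete knowledge across two operators. At 72 patients over the expected 36 months, about two a month, one block lasts about ten months. This stands, so the figures are ceilings. Memory is not the only route, however: the registry records stent type and is open to the investigators. The documents do not say whether the consultants are among them.
- No decision-maker or envelope opener is named. That the operator judges eligibility is the natural reading of a decision made during endoscopy, but it remains an inference.
- Consent and histology come first, and the remaining check concerns tumour site and length and expected stent position. Randomising after that check is the protective order. This narrows the room for discretion but does not close it, because whether stenting is needed and whether overlap will result are still judgements.

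A reader might also infer that selection is happening or likely. The documents do not support that: a usual-practice preference that also depends on availability is not evidence of conduct in the trial.

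**Conclusion.** The point holds as a modest, preventable weakness in allocation concealment. A fully informed operator could know about 5.5 of 72 allocations and guess about 61%; with partial knowledge the guessing falls toward 50%. It matters because four features coincide: a fixed disclosed size, unmasked operators, a late eligibility judgement, and a recorded stent preference. The result rests on the assumption that the operator, or someone advising the operator, makes that judgement.

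A reader might take the unequal split to mean that the planned sample size cannot be met. It does not mean that. The 36 per arm is a requirement from the power calculation, and the worst split costs at most about 0.5 points of power. An exact 72-place list is not needed, and it would not guarantee 36 analysable patients per arm, since one inclusion criterion (stent position once deployed) can only be checked after allocation.

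**What to change.** - In Interventions, replace the stated block size with permuted blocks of randomly varied size. Keep the sizes similar to the present one (for example 16 to 22), hold them in a document outside the protocol, and do not disclose them to the operators. Avoid small blocks.
- State who generates the list and who holds and opens the envelopes, preferably someone outside the unit, and that the envelopes are sequentially numbered.
- Require a time-stamped REDCap entry, made before the next envelope is opened, recording that the patient is eligible because stenting is required and OGJ overlap is expected. A later reversal, including one under the post-deployment criterion, is then visible.

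The cost is a regenerated list and one field in a registry that is already planned; no extra patients are needed. If recruitment has begun, the new list can start at the end of the current block. The limitation is that tally-based guessing stays at about 61–62%. The gain is that most certain allocations disappear and an eligibility decision cannot be changed unseen after allocation.

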Patients with palliative oesophageal cancer are in most instances frail and have a significantly limited life expectancy. It is thus imperative upon discharge, that further research-related follow-up should not inconvenience the patient nor have a negative effect on their quality of life. Furthermore, many of the patients treated at GSH have limited financial means to afford repeated follow-ups at the hospital. For these reasons, subsequent follow-up after discharge, will be done telephonically. Patients will be phoned at 1, 2, 4 and 8 weeks post stent insertion and will be asked about any symptoms related to the stent insertion, and have an assessment of symptomatic GOR using the GerdQ questionnaire ⁸, dysphagia, cough and pain levels at each telephonic follow-up. Telephonic follow-up of these patients will be done by the Clinical Coordinator, who is blinded to which type of stent the patient has received.

All patients will also be referred to the GSH Palliative Care Team. With any symptom reported by a patient or family member that is deemed to possibly require further intervention or treatment, the patient will be requested to return for an evaluation or appropriately managed according to the Palliative Care Distress Algorithm (Appendix 1). All complications will be managed as per standard treatment routinely employed for such a complication at GSH. Any such complications will be documented.

OUTCOME MEASURES

Primary Outcome Measure

The primary outcome will be patient-reported rates of symptomatic volume GOR and objectively measured volume GOR in both study groups. Patient-reported symptomatic volume GOR will be assessed using the validated GerdQ questionnaire (Appendix 2)⁸. This questionnaire has been chosen has it is simple, easy to understand and includes only 6 questions, which are all reflux-related. This questionnaire will be administered to the patient prior to the procedure, to establish a baseline. It will then subsequently be telephonically administered at the scheduled telephonic follow-ups at weeks 1, 2, 4 and 8. The GerdQ questionnaire enables the patient to provide a score at each follow-up interaction which can then be documented and the mean scores between the two groups can then be compared.

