GOR will also be objectively measured on day 1 post stent insertion using scintigraphy. The proposed protocol for scintigraphy is described in Appendix 3. This modality has been chosen as its accuracy compares favourably to pH monitoring⁹, but is much less invasive. It requires the patient to swallow a meal of soft, runny porridge and then undergo imaging. pH monitoring is invasive, requiring the insertion of an uncomfortable nasal probe which stays in-situ for 24 hours, increasing discomfort for the patient but also increasing the hospital stay by a further 24 hours. It is thus deemed inappropriate in this setting.

Secondary Outcome Measures

The secondary outcomes that will be assessed will include immediate technical success rate and any complications related to the stent insertion, subsequent stent-related complications, patient-reported dysphagia score prior to stent insertion, on day 1 post-insertion and then at each of the scheduled telephonic follow-ups and lastly, patient survival at 2 months post stent insertion. Dysphagia assessment will be done using the modified dysphagia scale first published by Mellow and Pinkas and validated for assessing dysphagia after metal stent insertion for oesophageal cancer (Appendix 4)²³. Furthermore, an assessment of the patient's pain level and whether they are coughing will also be documented, using validated pain²⁴ and cough scores²⁵ and pain (Appendix 5 & 6).

Data Collection

The following data parameters will be collected:

- Age
- Gender
- Performance status25 and BMI of the patient at time of stent placement
- Histological type of malignancy (e.g. adenocarcinoma, squamous cell carcinoma or other)
- Reason for inoperability: metastases, locally advanced or poor performance status
- Position of oesophageal malignant stricture (endoscopic measurement in centimetres from the incisors)
- Patient-reported degree of dysphagia prior to stenting
- Patient-reported GerdQ score pre-stenting
- Stent characteristics: anti-reflux vs conventional, length, diameter and brand name of stent
- Immediate technical success rate
- Immediate stent insertion complications:
 - o Bleeding
 - Perforation
 - o Other

- Subsequent stent-related complications during the follow-up period:
 - o Bleeding
 - Perforation
 - Migration
 - Stent occlusion and cause thereof
 - \circ Other
- Quantitative assessment of volume reflux as per scintigraphy (on day 1)
- GerdQ score at follow-up at week 1, 2, 4 and 8

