This trial will not involve a pharmaceutical product or device that requires repeated administration. Both stents are inserted as a once-off procedure and unless there is an unforeseen complication (such as stent migration or patient intolerance of the stent necessitating removal), these stents usually stay in-situ indefinitely. With the unfortunately short life expectancy for this group of patients, most participants will require a single stent insertion and will then die with the stent still in-situ. This means that once the trial period is over, they will still continue to have the benefit of the stent regardless of when the trial ends. If the anti-reflux stents are proven to significantly reduce GOR, those participants in the conventional stent group will however not be offered an anti-reflux stent if the stent they have received is still functional and without problems. This is because the procedure of exchanging one stent for another carries significant risks and in this vulnerable group of patients such a stent exchange procedure would not be justified.

Statistical Analysis

Data will be captured using the REDCap electronic data capturing software licensed to the University of Cape Town. All data exploration and analysis will be done using an appropriate statistical software programme such as SPSS (version 27.0, IBM, USA). Statistical significance will be set as p <0.05. Recorded data will be expressed as mean (SD), or median (interquartile range) when non-normally distributed (continuous data). Where continuous data are non-normally distributed, variables will be logarithmically transformed prior to inclusion in multivariable statistical analysis. Dichotomous variables will be expressed as proportions or percentages. Baseline demographic and clinical characteristics between the anti-reflux stent and the conventional stent group will be compared using appropriate statistical tests based on the nature of the data as well as distribution thereof. GOR scores between the two groups will be assessed using inferential statistics with the hypothesis that the anti-reflux stent group will have reduced reflux compared to the conventional stent group. In addition, survival analysis will be performed with visual representation using Kaplan Meier curves.

Sample Size

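### GerdQ is measured before stenting and at four follow-ups, but the plan does not say which visit or summary carries the primary test, whether baseline enters it, or how deaths are handled

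*Combined protocol and SAP*

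**What the plan says.** Under Primary Outcome Measure, GerdQ is "administered to the patient prior to the procedure, to establish a baseline". The same section continues: "It will then subsequently be telephonically administered at the scheduled telephonic follow-ups at weeks 1, 2, 4 and 8". Data Collection lists "GerdQ score at follow-up at week 1, 2, 4 and 8" as well as a pre-stenting score, and Appendix 7 has a field for each.

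The analysis is described in three places:
- Primary Outcome Measure: "the mean scores between the two groups can then be compared".
- Statistical Analysis: "GOR scores between the two groups will be assessed using inferential statistics".
- Sample Size: a two-group comparison of means, "with GerdQ score means as the primary outcome assessed", with 9 against 7 points, SD 3, alpha 5% and power 80%, giving 36 per arm.

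The type of outcome varies. Primary Objective/Hypothesis to be Tested sets out to "compare rates of self-reported, symptomatic volume GOR", and Primary Outcome Measure opens with "The primary outcome will be patient-reported rates of symptomatic volume GOR". Sample Size uses means. The text supplied contains no GerdQ cut-off that would turn a score into a rate.

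Statistical Analysis also plans a between-arm comparison of baseline characteristics, and requires non-normal continuous variables to be log-transformed before any multivariable analysis. It names no model and no covariates.

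**The concern.** Each patient can contribute a baseline and four follow-up scores, yet the stated test uses one score per arm and patient at an unspecified time. Week 1, 2, 4 or 8, an average over visits, a change from baseline, or a proportion above some cut could each be presented as the planned analysis.

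The choice could be made with data in view. Trial Design says the authors are not blinded to stent type, and Time Frame schedules interim analyses at 12 and 24 months. Blinding the patient and the telephone coordinator protects the collection of scores, but not the later choice of contrast.

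Two further things are at stake. A baseline already being collected may be left out of the outcome comparison. And in a population with short survival, the choice of visit decides how many patients contribute and what the comparison means once some have died.

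**Working it through.** **Inputs.** From Sample Size: difference 2, SD 3, alpha 0.05 (two-sided is implied, since only that gives 36), 36 per arm. From the opening background text: median survival 15 weeks from diagnosis, and 10.7 weeks with complete obstruction. Assumed, because the documents give neither: the correlation between visits (r) and between baseline and follow-up (b).

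**1. The plan's own figure.** n per arm = 2 × (1.960 + 0.842)² × 3² / 2² = 35.3, so 36 per arm and 72 in all. Power at 36 per arm: 2 / (3 × √(2/36)) = 2.828, and Φ(2.828 − 1.960) = 80.7%. The t-distribution gives 79.7%. The stated figure reproduces as a single unadjusted comparison with complete data.

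**2. Four visit tests left open.** With independent tests the chance of at least one false positive would be 1 − 0.95⁴ = 18.5%. Simulation of 40,000 null trials per setting, 36 per arm, equal correlation between visits, complete scores:

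| r | At least one p < 0.05 |
|---|---|
| 0.9 | 9% |
| 0.7 | 13% |
| 0.5 | 16% |
| 0.3 | 17% |

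Adding deaths takes the top of the range to 18%.

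**3. Baseline adjustment alone, one complete visit.** The residual SD is 3 × √(1 − b²).

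| b | SD | Power (normal approximation) | Gain, points |
|---|---|---|---|
| 0 | 3.00 | 80.7% | 0 |
| 0.2 | 2.94 | 82.3% | 1.6 |
| 0.3 | 2.86 | 84.3% | 3.5 |
| 0.5 | 2.60 | 90.4% | 9.7 |

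**4. Averaging four complete visits, no baseline, constant 2-point effect.** The SD of a patient's average is 3 × √((1 + 3r)/4).

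| r | SD | Power (normal approximation) | Gain, points |
|---|---|---|---|
| 0.9 | 2.89 | 83.7% | 2.9 |
| 0.7 | 2.64 | 89.5% | 8.7 |
| 0.5 | 2.37 | 94.7% | 14.0 |

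With both steps the variance factor is (1 + 3r)/4 − b². At r = 0.7 and b = 0.3 it is 0.775 − 0.090 = 0.685, and power is 92.8%.

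**5. Source of the gain.** In simulations with deaths, a mixed model for the visit average gave 86–95% power (15-week median) and 85–94% (10.7-week median). A plain t-test on each patient's mean available score gave 85–94% and 84–93%. The model adds −1 to +2 points, or about +10 at b = 0.5. Most of the gain therefore comes from the choice of summary.

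**6. Why the visit matters.** For illustration, take exponential deaths from stenting. Survival to week 8 is 0.5^(8/15) = 69% or 0.5^(8/10.7) = 60%, leaving about 24.9 or 21.4 patients per arm. An unadjusted week-8 t-test then has about 63% or 57% power.

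**7. Limits of an average.** If the effect wanes as 2, 2, 1, 0 points, the average is (2 + 2 + 1 + 0)/4 = 1.25. Simulated power is then 58–60% (15-week median) or 55–59% (10.7-week median), while week 8 shows no difference.

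**The case against.** The strongest reply is that the sections, read together, already point to mean GerdQ as the patient-reported outcome. On that view, *rates* is loose wording, baseline characteristics are compared between arms, and multivariable analysis is foreseen. Much of this stands. It would be too strong to say that the baseline goes unused altogether; the accurate statement is that no use of baseline GerdQ in the outcome comparison is stated. A rate is better seen as a wording conflict to settle than as a rival analysis the plan has adopted. Neither reply supplies a visit, a summary, a covariate or a rule for deaths.

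A second reply is that the false-positive range assumes success would be claimed if any one of four tests passed. The documents do not say so. The range bounds what the open wording permits and does not predict what the investigators will do.

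A third is that the benefit should not be credited to a mixed model. That stands, as step 5 shows. Baseline GerdQ is also taken before both the stent and the proton pump inhibitor prescribed after the procedure, so it may predict later scores poorly and the gain from adjustment may be near zero.

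Finally, treating scores after death as missing at random describes a hypothetical in which patients who die go on scoring. A while-alive summary is also defensible. This is a reason to state the assumption and test it, not a reason to leave the point open.

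**Conclusion.** The concern holds as a gap in pre-specification. The plan does not fix the patient-reported primary contrast, state any use of baseline GerdQ in it, or say how scores missing through death are handled. The main benefit of repair is a test fixed in advance; power is secondary.

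Size: up to about a 9–18% chance of at least one false positive if any visit could be claimed; a gain of 0 to about 10 power points from baseline adjustment; and about 3 to 14 from averaging. The gains assume complete data, and the averaging gain also a constant 2-point effect. All three rest on correlations the documents do not give.

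Three stronger inferences are not supported:
- That the trial is underpowered as designed. Its 80% reproduces for one complete comparison of means.
- That the week-8 figures forecast this trial. One median runs from diagnosis and the other applies only to complete obstruction, so neither describes survival from stenting in the enrolled population.
- That fixing this contrast controls all false-positive risk. Day-1 scintigraphy, the other half of the primary outcome, and the two interim analyses are separate points that it leaves open.

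**What to change.** Amend Primary Outcome Measure and Statistical Analysis as follows:

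1. Name one patient-reported primary contrast: the between-arm difference in mean GerdQ, averaged with equal weight over weeks 1, 2, 4 and 8, by assigned arm, with a 95% CI.
2. Estimate it from a repeated-measures linear model with visit, treatment, treatment-by-visit and baseline GerdQ. The covariance structure and degrees-of-freedom method are for the trial statistician to choose and write down.
3. Report the four visit-specific differences as supporting results, so that a waning effect is visible.
4. State that this mean, not a rate, is the patient-reported primary analysis, and align the wording of the objective and outcome sections.
5. Exempt this analysis from the log-transform rule in Statistical Analysis. The 2-point difference is on the original scale, and the Appendix 2 scoring allows a total of 0, which has no logarithm.
6. State that scores after death are treated as missing at random, and add one sensitivity analysis for death, such as a while-alive mean of available scores or a worst-rank comparison.
7. Keep 72 patients.

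The cost is wording and a standard procedure in statistical software; no new data, visits or patients are needed. There are three downsides. The gain may be near zero if baseline predicts poorly. An average can hide a waning effect. Missing-at-random handling reduces bias from deaths without removing it: in simulations where the death hazard doubled per SD of the next score, a true week-8 difference of 2.0 was estimated as 1.84–1.88 (15-week median) or 1.78–1.81 (10.7-week median), against 1.76–1.78 or 1.66–1.70 from the raw comparison.
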